### Primary objective:

The study has four aims.

1. To compare the psychometrics of digital and paper-pencil cognitive tests. Score distributions, test-retest reliability, and construct validity of the following tests will be compared: Trail Making Test (TMT), Rey Osterrieth Complex Figure Test (ROCFT), Digit Span Test, Controlled Oral Word Association Test (COWAT), Category Fluency Test, Rey Auditory Verbal Learning Test (RAVLT), Clock Drawing Test, Star Cancellation Test, O Cancellation Test, Mini Mental Status Exam 2 (MMSE-2).
2. To assess the degree of agreement between the algorithm and manual scores for the digital Rey Osterrieth Complex Figure Test and Clock Drawing Test.
3. To estimate regression-based norms and reliable change indices.
4. To estimate factor loadings for a structural equation model describing cognition in terms of distinct cognitive domains.

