### Primary hypotheses

The following primary hypotheses will be tested in the study:

Aim 1.

- A. Digital and paper-pencil normed test scores are comparable. We consider the two versions of a test comparable when the digital normed score is on average within .3 sd of the paper normed score and the two normed scores correlate at least .6.
- B. Test-retest reliability of the digital tests is comparable to test-retest reliability of the paper-pencil tests. We consider the reliability to be comparable when we observe no significant difference in a z-test between the digital and the paper-pencil test-retest correlations.

Title: Clinical Investigation Plan		Author: [name]		Company Restricted	
DocID: ICBE-2-28674	Version: 2.0	Date: 2019-02-18	Status: Approved	Page: 20 of 35	
IRBMANAGER PILOT – QI PROJECT					

C. Construct validity of the digital tests is comparable to the construct validity of the paper-pencil tests. We consider construct validity to be comparable when confirmatory factor analysis yields the same factor structure for digital and paper-pencil tests.

Aim 2.

D. The score(s) provided by the ROCFT and Clock Drawing Test scoring algorithms on ISC are correlated highly (> .8) to the score provided by manual scoring for the same drawings.

Aims 3 & 4 have no accompanying hypotheses.

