**6 CLINICAL INVESTIGATION DESIGN**

**6.1 General**

The study has a randomized, counterbalanced design and consists of two phases (see figure 1). We sample participants according to the sampling plan outlined below, to ensure representativeness of the sample. We will oversample by 20% to account for dropout or incomplete data (the *n*'s below represent the desired cell counts, after dropout).

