**Figure 1. Schematic overview of study design.**

Title: Clinical Investigation Plan		Author: [name]		Company Restricted	
DocID: ICBE-2-28674	Version: 2.0	Date: 2019-02-18	Status: Approved	Page: 21 of 35	
IRBMANAGER PILOT – QI PROJECT					

Group	A	B	C	D	E
n	100	100	50	50	100-150
Phase 1 tests	Digital	Paper-pencil	Digital	Paper-pencil	Digital
Phase 2 tests	Paper-pencil	Digital	Digital	Paper-pencil	

All participants of Group A-D in phase 1 will be invited to participate in two assessments that will take place with a time interval of four-five weeks between the two phases to minimize retest effects. Participants will be randomly assigned with minimization for demographic variables (to make sure that the groups do not differ in terms of gender, age, education level, and ethnicity) to one of the following groups:

- Group A ( $n=100$ ) completes digital tests in phase 1 and paper-pencil tests in phase 2,
- Group B ( $n=100$ ) completes paper-pencil tests in phase 1 and digital tests in phase 2,
- Group C ( $n=50$ ) completes digital tests in both phases,
- Group D ( $n=50$ ) completes paper-pencil tests in both phases,
- Group E ( $n=100-150$ ) only completes digital tests in one phase (50% of group E will be enrolled in phase 1 and the other 50% of group E will be enrolled in phase 2).

The data of group A and B are used to compare score distributions within-subjects

The data from groups A-D (phase 1) are used to compare score distributions between-subjects (aim 1).

The data of group C and D are used to assess and compare test-retest reliability (aim 1) and assess reliable change indices (aim 3).

The data of group A (phase 1), group C (phase 1) and group E are used to estimate regression based norms for the digital tests (aim 3), as well as to estimate factor loadings for the structural equation model (aim 4).

The data of group A (phase 1), group B (phase 1), group C (phase 1) and group D (phase 1) are used to compare construct validity (aim 1).

Participants will be randomized with minimization for demographic variables (gender, age, education level, ethnicity).

The purpose of adding the 100-150 participants in Group E is to increase the sample size of participants who completed the digital tests for the first time for the norm data to 250-300.

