**Aim 1 comparison of psychometrics.**

Hypothesis A: Digital and paper-pencil test scores are comparable.

For each test, we will first compute age-only referenced scores for digital and paper-pencil version separately. Referenced scores are computed based on the regression based norms (procedure described below under aim 3) and are represented as z-scores indicating a participant's deviation from what would be expected based on the norm sample for a participant with identical demographic characteristics. We then compute the correlation between digital and paper-pencil referenced scores within participants in group A and B (which are the groups in which participants completed both digital and paper-pencil versions of the tests), which needs to be  $r > .6$  to be considered comparable. Our planned sample size allows us to detect a correlation of  $r > .2$  with 80% power. We also perform an equivalence test for each test, comparing the distribution of digital normed scores with paper-pencil normed scores, using a two-one-sided-t-test approach (TOST; Schuirmann, 1987), with equivalence bounds of  $\pm .3$  sd, which we have 99% power to detect. Our planned sample size would allow us to detect equivalence with bounds of at least  $\pm .21$  with 80% power.

Hypothesis B: Test-retest reliability is comparable.

Test-retest reliability will be tested by examining for each test the correlation between the digital tests in phase 1 and phase 2 (group C) and comparing this to the correlation between the paper-pencil tests in phase 1 and phase 2 (group D). High test-retest correlations are expected ( $r > 0.7$ ), except for the ROCFT copy condition, since the scores of this condition generally show a moderate ceiling effect. The planned sample size for group C and group D each yield 80% power to detect  $r > .37$ .

Hypothesis C: Construct validity is comparable.

Construct validity will be investigated by means of two confirmatory factor analyses (CFA), one for each group (digital vs. paper-pencil). We expect to see that the factor structure that fits the paper-pencil data (phase 1, group B & D) well, will also fit the digital data (phase 1, group A & C) well. Assuming that at most two variables per test are included in the CFA, the subject-to-variable ratio is near 10:1 for each CFA.

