**Aim 4. Estimate factor loadings for cognitive model describing**

We have developed a model of cognitive functioning using the latent variable part of structural equation modelling (which is identical to the CFA described above). We will fit the ISC model of cognitive functioning on the digital test data from Group A, C, and E, yielding a sample of 250 (up to 300) participants for the CFA, further increasing the subject-to-variable ratio to ~12:1.

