**Pass/fail criteria**

Please see above description.

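### The two stated subject-to-variable ratios for the CFAs, near 10:1 for Aim 1 and ~12:1 for Aim 4, cannot both hold for one set of variables, and the variable count is not given

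*Combined protocol and SAP*

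**What the plan says.** Section 7, Aim 1, hypothesis C plans two confirmatory factor analyses on phase 1 data, one for paper-pencil (groups B and D) and one for digital (groups A and C). The sample-size support is one sentence: "Assuming that at most two variables per test are included in the CFA, the subject-to-variable ratio is near 10:1 for each CFA".

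Section 6.1 sets groups A and B at 100 and groups C and D at 50, and says that these numbers "represent the desired cell counts, after dropout". The primary objective in section 5 introduces its list of ten tests with "Score distributions, test-retest reliability, and construct validity of the following tests will be compared".

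Section 7, Aim 4 equates the latent-variable part of its model with the CFA already described. It fits the model to the digital data of groups A, C and E, "yielding a sample of 250 (up to 300) participants for the CFA, further increasing the subject-to-variable ratio to ~12:1".

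On the decision rule, section 5 says: "We consider construct validity to be comparable when confirmatory factor analysis yields the same factor structure for digital and paper-pencil tests". Section 7 words the matter as an expectation ("We expect to see that the factor structure that fits the paper-pencil data" well will also fit the digital data well). The Pass/fail criteria entry reads only "Please see above description".

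**The concern.** The Aim 1 ratio does not follow from the inputs given beside it unless some tests contribute fewer than two variables or are left out, and the plan does not say which. The Aim 4 sentence presents its ratio as an increase on the Aim 1 ratio, which invites the reader to assume one variable set. The two figures then contradict each other.

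The ratio is the only sample-size support stated for hypothesis C, a primary hypothesis under the aim that backs the product claim of similar psychometrics for digital and paper tests. A reader who relies on it should be able to reproduce it.

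**Working it through.** **Inputs**
- Tests compared: TMT, ROCFT, Digit Span, COWAT, Category Fluency, RAVLT, Clock Drawing, Star Cancellation, O Cancellation and MMSE-2, so 10 (section 5).
- Variables per test: at most 2 (section 7, Aim 1). Cap = 10 × 2 = 20.
- Participants per Aim 1 CFA: A + C = 100 + 50 = 150; B + D = 100 + 50 = 150 (section 6.1, net of dropout).
- Participants for Aim 4: A + C + E = 100 + 50 + 100 = 250, or 300 if group E reaches 150.

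**Formula:** ratio = participants / variables.

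| Variables | Aim 1, n = 150 | Aim 4, n = 250 | Aim 4, n = 300 |
|---|---|---|---|
| 14 | 10.7 | 17.9 | 21.4 |
| 15 | 10.0 | 16.7 | 20.0 |
| 16 | 9.4 | 15.6 | 18.8 |
| 18 | 8.3 | 13.9 | 16.7 |
| 20 (cap) | 7.5 | 12.5 | 15.0 |
| 21 | 7.1 | 11.9 | 14.3 |
| 22 | 6.8 | 11.4 | 13.6 |

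**Reproducing the stated figures.** Allowing ±1 on each ratio, near 10:1 at n = 150 needs 14 to 16 variables. About 12:1 needs 20 to 22 variables at n = 250, or 24 to 27 at n = 300, which is above the cap. The ranges do not overlap.

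**Check that does not depend on counting tests.** For any common variable count, Aim 4 ratio / Aim 1 ratio = 250/150 = 1.67 (300/150 = 2.0 at the larger group E). The stated figures give 12/10 = 1.2.

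**Attempts to reconcile them**
- Oversampling: if all of the 20% extra completed, Aim 1 would be 180/20 = 9.0, but Aim 4 would be 300/20 = 15.0. The stated group sizes are after dropout in any case.
- Leaving out MMSE-2 (9 tests, 18 variables): 8.3 and 13.9.
- Adding the paper-only naming test (11 tests, 22 variables): 6.8 and 11.4.
- 200 participants over 20 variables gives exactly 10:1, but the plan assigns 200 to neither CFA.

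**Does the ratio bear on whether 150 is enough?** As an illustration, assume 5 correlated factors with simple structure. Degrees of freedom are p(p + 1)/2 − (2p + 10): 210 − 50 = 160 at 20 variables and 120 − 40 = 80 at 15. With n = 150 and alpha .05, the noncentral chi-square power to separate RMSEA .05 from .08 is .96 and .79 respectively. The larger model, with the lower ratio, has the higher power.

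**How much would the fit cut-off matter?** Same assumptions, 20 variables, two independent samples of 150. The table gives the chance that both formats fall below the cut-off.

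| Population RMSEA (assumed) | Cut-off .06 | Cut-off .08 |
|---|---|---|
| .04 | 96% | 100% |
| .05 | 75% | 100% |
| .07 | 2% | 80% |
| .09 | 0% | 1% |

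At 15 variables and RMSEA .07 the figures are 5% and 67%.

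**The case against.** The strongest reply is that two variables per test is a maximum. Some tests may supply one variable, and section 7 does not say that all ten enter the CFA. Fifteen variables satisfies the assumption and gives exactly 10:1, so the Aim 1 sentence taken alone is not a wrong division. This stands: 7.5:1 is a floor, not the plan's value. It does not clear the plan, because 15 variables puts Aim 4 at 16.7:1 rather than ~12:1.

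A second reply is that Aim 4 may call its model identical in method only, with a different set of variables. That reading is possible, so the contradiction is conditional. But presenting ~12:1 as a further increase makes a common set the natural reading, and no second set is mentioned.

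A third is that a rule-of-thumb ratio changes no sample size or analysis. That is fair and limits the weight of the point.

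A reader might also infer that hypothesis C has no rule, or that a cut-off chosen late would decide it. The documents do not support either. Section 5 gives a rule (same factor structure), and fitting well appears only in section 7, as an expectation. The cut-off has a large effect near a population RMSEA of .07, which lies midway between the two cut-offs compared, and little effect when fit is clearly good or clearly poor. The population fit is unknown; section 3 reports excellent fit in a pilot of 148 people but gives no index.

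**Conclusion.** The concern holds as an inconsistency in the stated figures. At the plan's cap the Aim 1 ratio is 7.5:1, 25% below the 10:1 quoted. The Aim 4 figure points to about 20 variables and hence to about 7.5:1 for Aim 1. If both models use one variable set, at least one stated ratio is wrong; if they do not, the plan leaves that out. The division is certain. The contradiction rests on the common-set reading, which the wording favours but does not prove.

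It would be tempting to conclude that the Aim 1 CFAs are too small. The documents do not support that: they set no minimum ratio, and the illustration above, under its assumed five factors, shows no shortfall caused by the lower ratio. The absence of a named fit index and cut-off is a secondary and minor point.

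**What to change.** 1. State how many variables enter the Aim 1 CFAs and the Aim 4 model, and whether the sets are the same. Section 3 reports that the mappings were already fitted to pilot data, so the count should be available.
2. Restate both ratios from that count. With 20 variables: 7.5:1 for Aim 1 and 12.5:1 for Aim 4 (15:1 at n = 300). With 15 variables: 10:1 and 16.7:1 (20:1 at n = 300).
3. Advisable, and smaller: name before analysis the fit index and cut-off that will be used in both formats to judge whether the structure is the same.

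The cost is one variable count, two corrected figures and one added sentence. No participants or data are added. The downsides are that the stated support may read lower, and that a cut-off fixed in advance leaves less room for judgement on hypothesis C.

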**Aim 2 Agreement between algorithm and manual scoring**

Hypothesis D: The score(s) provided by the ROCFT and Clock Drawing Test scoring algorithms on ISC are correlated highly ( $> .8$ ) to the score provided by manual scoring for the same drawings.

For each test with algorithmic scoring, agreement with manual scoring will be tested using the two-one-sided t-tests approach (TOST; Schuirmann, 1987) on the average correlation between the algorithm and each rater on the one hand and the average correlation between the rater and each other rater on the other. Before submitting the correlations to the TOST analysis, we apply Fisher's r-to-z transformation. We will use equivalence bounds of  $r \pm .1$  as a stringent criterion of practical equivalence, although we note that any correlation  $> .8$  provides sufficient support for our claim given that the algorithms may actually be more an improvement relative to manual scoring.

We used a simulation approach to estimate the sample size of raters needed to have 80% power to detect equivalence in agreement using TOST. This approach is described in detail in Technical Note PR-TN2018/0033 (Dotsch & Klaming, 2018). For the ROCFT, the simulation approach has resulted in the recommendation that six raters will be required to score a random sample of 100 drawings from the test in order to derive at least 80% power with stringent equivalence bounds backing a strong claim of equivalence between raters and algorithm. We assumed that for the CDT a similar number of raters would be sufficient, given that scoring of drawings from both tests have generally high inter-rater agreement.

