We will use the 100 sets of digital ROCFT and Clock Drawing Test drawings, randomly drawn from the full sample, to establish agreement between scoring algorithms and manual scoring by well-trained raters (aim 2).

Title: Clinical Investigation Plan		Author: [name]		Company Restricted	
DocID: ICBE-2-28674	Version: 2.0	Date: 2019-02-18	Status: Approved	Page: 22 of 35	
IRBMANAGER PILOT – QI PROJECT					

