## 7 STATISTICAL CONSIDERATIONS

**Statistical design, analyses and power considerations**

Below we describe the planned analyses for each aim and hypothesis. The tests are scored by two raters (with 30% overlap) and inter-rater agreement is assessed prior to proceeding with the following analyses. All correlations mentioned below are Pearson correlations. Retest correlations are corrected for the variability of the normative sample (Allen & Yen, 2002; Magnusson, 1967). Correlation between paper and pencil measures are corrected for measurement error (Padilla & Veprinsky, 2012). In our power analyses we assume an alpha of .05.

Title: Clinical Investigation Plan		Author: [name]		Company Restricted	
DocID: ICBE-2-28674	Version: 2.0	Date: 2019-02-18	Status: Approved	Page: 25 of 35	
IRBMANAGER PILOT – QI PROJECT					

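### The Aim 2 equivalence test states no unit or standard error; run over six raters, it would omit the error of the 100 shared drawings and not hold its 5% level

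*Combined protocol and SAP*

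**What the plan says.** Section 7, Aim 2, applies a TOST to "the average correlation between the algorithm and each rater on the one hand and the average correlation between the rater and each other rater", after Fisher's r-to-z transformation, with bounds of r ± .1. A simulation was used to "estimate the sample size of raters needed to have 80% power to detect equivalence in agreement using TOST". For the ROCFT the result was: "six raters will be required to score a random sample of 100 drawings from the test in order to derive at least 80% power". The plan describes what this sizing is meant to secure as "stringent equivalence bounds backing a strong claim of equivalence between raters and algorithm". The same number of raters is carried over to the Clock Drawing Test. The simulation is described in a technical note that is cited but is not part of the documents.

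Section 6.1 says the material will be "100 sets of digital ROCFT and Clock Drawing Test drawings, randomly drawn from the full sample". At the start of section 7: "In our power analyses we assume an alpha of .05".

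The section 5 hypothesis for Aim 2 (Hypothesis D) is different: the algorithm score must correlate above .8 "to the score provided by manual scoring for the same drawings". Section 7 adds that any correlation above .8 is enough support for the claim.

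Section 7 does not say what the n of the TOST is, whether the two sets of correlations are paired, how the standard error is formed, what the degrees of freedom are, or how a margin written in r becomes a margin in z.

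**The concern.** The sample size of this test is counted in raters, so an analyst would most naturally give each rater two values (Fisher z with the algorithm, and mean Fisher z with the other five raters) and run a t-test over six raters. All six pairs of values come from the same 100 drawings and the same single set of algorithm scores. If those drawings happen to flatter the algorithm, all six algorithm–rater correlations rise together. The spread between raters does not register this shared movement, so a standard error built from it is too small.

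In an equivalence test, too small a standard error makes it too easy to declare equivalence. An algorithm sitting exactly on the margin could then earn the stronger claim well above the nominal 5% of the time. Section 2.3 says the study data will be used to assess the equivalence of automatic and manual scoring, so the claim is one the sponsor intends to be able to make.

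**Working it through.** **Inputs from the plan.** Six raters, 100 drawings, Pearson correlations, Fisher z, bounds r ± .1, alpha .05 (taken as one-sided .05 for each of the two tests), stated power at least 80%.

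**Assumed.** Inter-rater r of .80–.95 (the plan calls agreement generally high but gives no figure), rater reliabilities equal or spread by up to ±.15, and a one-factor normal model.

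**Model.** T ~ N(0,1); score of rater i = √rel_i·T + error. The algorithm's loading is set so that its mean correlation with the raters is the mean inter-rater r minus .1. Then zA_i = atanh r(algorithm, rater i) and zR_i = mean of atanh r(rater i, each other rater). The TOST is on mean(zA) − mean(zR), paired (5 df) or unpaired (10 df), with 4,000–6,000 simulated studies per error cell.

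**Step 1: the plan's 80% power.** It cannot be reproduced, because the inputs are not given.
- Margin on the r scale, equal raters: three raters already give 95–100%.
- Margin of .1 in z units, equal raters: six raters give about 66–76% (paired) or 57–69% (unpaired).
- Six raters are just enough for the unpaired test at, for example, r .80 with spread ±.175 (73% with five, 82% with six) or r .60 with spread ±.10 (74% and 82%).

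**Step 2: the margin in z.** Lower bound = atanh(r − .1) − atanh(r).
- r = .80: .867 − 1.099 = −.231
- r = .90: 1.099 − 1.472 = −.374
- r = .95: 1.256 − 1.832 = −.576

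**Step 3: standard error against true variability.** With equal raters, the rater-based SE averages .019–.028, while the true SD of the mean difference is .066–.075. The SE is 2.3–4.0 times too small. A hand check for the paired test uses SE ≈ .02 and SD ≈ .07. The test passes when the difference exceeds the bound by 2.015 × .02 = .040, which is .040/.07 = .58 true SDs. The chance of that at the margin is 1 − Φ(.58) ≈ 28%, not 5%.

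**Step 4: simulated false equivalence, algorithm exactly .1 worse, r-scale margin.**

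| Raters | Paired | Unpaired |
|---|---|---|
| Equal, r .80 / .85 / .90 / .95 | 24.8 / 27.0 / 29.2 / 34.0% | 21.8 / 23.9 / 28.1 / 32.8% |
| Random spread ±.08, r .80 / .85 / .90 | 24.0 / 25.1 / 22.9% | 14.6 / 13.5 / 10.4% |
| Random spread ±.15, r .80 | 23.2% | 8.2% |
| Fixed even spacing ±.08, r .80 / .85 / .90 | 23.5 / 22.7 / 15.6% | 9.8 / 7.0 / 2.2% |

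**Step 5: sensitivity.**
- Section 7, Aim 1, says of the ROCFT copy condition that "the scores of this condition generally show a moderate ceiling effect". With 30% of scores at ceiling, the error is 26–28% paired and 23–26% unpaired.
- Twelve raters (equal): 33–39% paired. Adding raters shrinks the reported SE but not the shared error.
- 200 or 400 drawings (equal raters): 25–31% paired. More drawings shrink both in proportion, so the level does not improve.
- Margin in z units with very unequal raters: the unpaired test falls to 2–6%, and below 1% at the largest spread tried.

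**Step 6: how often Hypothesis D would also be met.** With equal raters, the TOST passing together with a mean algorithm–rater correlation above .8 occurred in 0.3% of simulated studies at inter-rater r .80, 7% at .85, 27–28% at .90 and 33% at .95.

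**The case against.** **The plan does not state the test examined here.** This is correct. The six-rater t-test is inferred from the sizing in raters, and the technical note may define a standard error that already covers drawings. What the text itself establishes is that unit, SE, df and margin scale are missing.

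**The equal-rater cases do not match the plan's sizing.** Also fair. If raters were equal and the margin on the r scale, three would have been enough. In the two settings of Step 1 where the unpaired test needs six raters, its error is 6.7% (r .80, spread ±.175) and 15% (r .60, spread ±.10); the paired test gives 22.5% and 21%. The setting closer to high agreement is therefore near nominal for the unpaired test. A reader might infer that every version of the test is inflated. The figures do not support that: the unpaired range includes 5%.

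**The target of inference could be raters only.** If the drawings and algorithm scores are treated as fixed, the error is 2–4% unpaired and 5–14% paired. But the plan draws the drawings at random from the full sample, which points to inference beyond those 100.

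**A reader might conclude that Aim 2 as a whole is at risk.** The documents do not support this. Hypothesis D is the only stated Aim 2 hypothesis, section 7 treats a correlation above .8 as sufficient, and Step 6 shows that D stops most false passes below about .90.

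**A reader might also object that the upper bound r + .1 does not exist once inter-rater r reaches .9.** This does no harm to the error rate, since no correlation can exceed such a bound.

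**Conclusion.** The concern holds as a fault in how the equivalence test is specified, with a conditional size. If the TOST is run over six raters, its standard error omits the error from the shared drawings and the single set of algorithm scores, and the 5% level is not controlled. With inter-rater r .80–.95, an r-scale margin and an algorithm exactly .1 worse, false equivalence is about 16–34% for a paired test. For an unpaired test it is about 21–33% with similar raters and falls to 5% or below with very unequal ones.

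The consequence is confined to the stronger equivalence claim, and it matters mainly when inter-rater r is about .90 or higher. The stated 80% power can be neither confirmed nor refuted. Confidence is medium, because the inter-rater correlation, rater spread and pairing are all assumed and the technical note is unseen. The item should be settled before analysis.

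**What to change.** In section 7, Aim 2:

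1. State the unit, SE and df of the TOST. If the technical note's SE already includes drawing-level variance, copy it in. Otherwise specify that the SE of the difference in mean Fisher-z correlations covers both drawings and raters. One option is SE² = delete-one-drawing jackknife variance + delete-one-rater jackknife variance, with t on 99 df; a bootstrap over drawings and raters would serve equally.
2. State that .1 is on the r scale and how it is converted. With rA and rR the back-transformed mean algorithm–rater and rater–rater correlations, one form in which both tests can always be computed is: atanh(rA) − atanh(rR − .1) > 0 and atanh(rA − .1) − atanh(rR) < 0, each one-sided 5%.
3. Restate the power under that SE.

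Keep the six raters, the 100 drawings and Hypothesis D.

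**Cost.** Wording and analysis code only.
- Error at the margin with the combined SE was 2.0–5.7% in the settings tabulated above and in the ceiling and Step 1 settings. With wider rater spread (SD .2 of the rater loading on the z scale) it was still about 9–11%, so across all r-scale settings allow for up to about 11%.
- Power for an algorithm as good as a rater is about 98–100% for r .80–.95 with spread up to ±.08. It falls to 89% at r .80 with spread ±.15, 81% at ±.175, and 48% if inter-rater r is only .60.
- An algorithm truly .05 worse passes less often: 46–50% at r .80 (70–83% with the rater-level test) and 86–89% at r .95 (96–99%).
- If .1 was meant in z units, power with 100 drawings is far below 80% (between 2% and 26% across the variants run), so the scale must be settled first.

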The ISC production equivalent that will be used for administering O Cancellation Test, Category Fluency Test, RAVLT, COWAT and Star Cancellation has the exact same patient interface as the end-product. The digital tests will be provided to the participants on an iPad Pro tablet (Apple). It has a screen size of 12.9-inches with a screen resolution of 2732x2048. This is the exact same tablet as required for use of the final ISC product.

Participants will use the Apple pencil for the iPad Pro tablet to perform the digital tests (see Figure 1). The tablet will present instructions for each test to participants via both written text and audio recordings. A researcher will observe in order to ensure that the participant understands and follows the instructions (see Figure 2). The iPad Pro tablet, Apple pencil and the regular laptop, which may be used by the researcher to take notes, are all CE marked devices.

Figure 1. iPad pro and Apple pencil used by the participant

Figure 2. Regular laptop used by researcher

The ISC production equivalent and ISC product (verified for data collection, SW version 1.0.0) are only utilized to collect data. The scoring algorithms for the ROCFT and the Clock Drawing Test have either not yet been implemented or the output of those that have been implemented will not be considered relevant. The data collected with the device during the clinical investigation will be used to assess the equivalence of outputs from automatic scoring by the algorithms to traditional manual scoring. Only when the output of the algorithms have high agreement with manual scores of the respective test, the algorithms will be integrated into the final ISC product.

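### Aim 2 compares algorithm and manual scores only by Pearson correlation, so a constant or linear scoring error would pass unseen, although section 2.3 speaks of equivalent outputs and high agreement

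*Combined protocol and SAP*

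**What the plan says.** Section 7 of the combined protocol and SAP opens with a general rule: "All correlations mentioned below are Pearson correlations". Under Aim 2 (Hypothesis D) it gives two criteria.

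- A TOST, after Fisher's transformation, compares "the average correlation between the algorithm and each rater on the one hand" with the average correlation among the raters. The bounds are ±.1 in r.
- A correlation above .8 "provides sufficient support for our claim given that the algorithms may actually be more an improvement relative to manual scoring".

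Six raters score 100 drawings chosen at random. For the ROCFT this is said to give at least 80% power "with stringent equivalence bounds backing a strong claim of equivalence between raters and algorithm". No mean difference, slope or absolute-agreement measure is planned between algorithm and manual scores, and the .8 threshold carries no confidence limit.

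Section 6.2 names the target as relative agreement: the algorithm should put examinees in the same order as the expert raters. The claim tied to Aim 2 in section 5 is that scoring is reproducible.

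Section 2.3 goes further. One sentence says the data will be used to judge whether automatic outputs are equivalent to manual scoring. The next sets the condition for the final product: "Only when the output of the algorithms have high agreement with manual scores of the respective test, the algorithms will be integrated".

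On norms, section 7 states: "The tests are scored by two raters (with 30% overlap) and inter-rater agreement is assessed prior to proceeding with the following analyses". Under Aim 1 it adds: "Referenced scores are computed based on the regression based norms (procedure described below under aim 3) and are represented as z-scores". Aim 3 specifies linear regression but does not say whether manual or algorithm scores enter it for these two tests. In use, section 3 has algorithms score the tests.

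**The concern.** A correlation shows whether two scorers rank people alike. It does not show whether they give the same number. An algorithm that marks every drawing low, or on a compressed scale, would meet both Aim 2 criteria as fully as an unbiased one, and could be integrated on that evidence under wording that speaks of equivalence.

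The practical stake is the normed score. If the norms come from manual scores and the product reports algorithm scores, a patient is compared with a reference set by a different scorer. The sponsor's own Aim 1 does not leave this gap: it pairs a correlation with a TOST on score levels at ±.3 SD. Aim 2 has only the first half.

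**Working it through.** **Inputs.** From section 7: Pearson correlations, 100 drawings, six raters, bounds of ±.1 in r, threshold .8, alpha .05. The documents give no inter-rater correlation, offset or scale error, so those values below are assumptions.

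**The plan's own figure.** Section 7 says "We used a simulation approach to estimate the sample size of raters needed to have 80% power" and refers to a technical note for the detail. The simulation inputs are not in the documents, so the 80% is neither confirmed nor refuted. Nothing below depends on it.

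**Step 1: linear errors are invisible.** Let the algorithm report A' = c + bA with b > 0. Then cov(A', R) = b·cov(A, R) and SD(A') = b·SD(A), so r(A', R) = r(A, R) for every rater R. The rater-rater correlations do not involve A. Both sides of the TOST, and the r > .8 comparison, are therefore unchanged. This is exact and needs no assumed figure.

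**Step 2: what an absolute measure would show.** With rater SD 1, algorithm SD b and offset d in SD units, Lin's concordance is 2rb / (1 + b² + d²). At an assumed r = .90:

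| Offset d | Scale b | Concordance | Pearson r |
|---|---|---|---|
| 0 | 1 | 1.80/2.00 = .90 | .90 |
| 0.5 | 1 | 1.80/2.25 = .80 | .90 |
| 1 | 1 | 1.80/3.00 = .60 | .90 |
| 0 | 0.7 | 1.26/1.49 = .85 | .90 |
| 1 | 0.7 | 1.26/2.49 = .51 | .90 |

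In simulation (100 drawings, six raters, inter-rater r .90, bounds read on the r scale, 1,000 runs per row), the TOST and the .8 rule passed in every run of all five rows.

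**Step 3: effect on normed scores.** A referenced score is z = (Y − fitted) / s.

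- *Algorithm scores build the norms.* The fitted value becomes c + b·fitted and the residual SD becomes b·s, so z' = b(Y − fitted) / (b·s) = z. Linear errors cancel.
- *Manual scores build the norms.* The error stays. An offset of −.1, −.2, −.3 or −.5 SD moves an average person to the 46th, 42nd, 38th or 31st percentile on that test. A scale of 0.7 turns a z of −2 into −1.4.
- *Domain level.* For k equally weighted measures with inter-measure correlation ρ, the shift is d / √(k[1 + (k − 1)ρ]). Assuming k = 2 to 4 and ρ = .3 to .5, an offset of .5 SD shifts the domain by .5/√10 = .16 to .5/√2.6 = .31 SD. Offsets of .1 to .3 SD shift it by .03 to .19 SD.

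**Step 4: the .8 rule as a point estimate.** For one algorithm-rater pair, SE(z) = 1/√97 = .1015. An observed r of .81 has a 95% interval of .730 to .868. The chance of observing r > .8 is 50% at true r .80, 30% at .78 and 11% at .75. With the six-rater average (simulation, inter-rater r .90) it is 51%, 30% and 9%.

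**Step 5: precision available for a level check.** With inter-rater r .90, an algorithm as good as a rater and the six raters taken as fixed, the SD of (algorithm − rater mean) is √(.1 + .1/6) = .342. The SE is .342/√100 = .034 and the 90% half-width is 1.66 × .034 = .06 SD.

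**The case against.** The strongest reply is that section 6.2 openly chooses ranking, Hypothesis D is itself a correlation, and the section 5 claim is reproducibility. The strong claim in section 7 can be read as equivalence in inter-rater correlation. Nothing in the documents suggests that either algorithm is biased. The algorithms are applied after data collection (sections 1 and 6.2), so norms built on algorithm scores remain possible, and section 7 allows norms to be updated.

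Most of this stands. Correlation is a sound tool for a ranking claim, and the harm is conditional. It does not answer section 2.3, whose wording about outputs and agreement with manual scores reaches beyond ranking.

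Three stronger readings are tempting and are not supported:

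- *Equivalence of outputs is itself the integration condition.* Section 2.3 uses two adjacent sentences, and the condition is worded as high agreement.
- *Normed scores will be wrong.* Section 7 leans towards manual norms, because two raters score the tests before the later analyses, but Aim 3 does not say so. The remark in section 2.3 that on-device algorithm output is to be disregarded concerns data collection and does not settle it.
- *The TOST is mis-sized or its bounds are faulty.* The replicate unit and the handling of the ±.1 bounds rest on a technical note outside the documents, so no such finding can be made.

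**Conclusion.** The concern holds in this limited form and should be fixed before the drawings are scored. As written, no Aim 2 criterion can detect a constant or linear difference between algorithm and manual scores, so the evidence supports rank agreement and not the broader wording of sections 2.3 and 7. That conclusion is algebraic.

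The size of any real error is unknown. The percentile and domain shifts above apply only if the norms are manual and the assumed offsets occur; with algorithm norms, linear errors cancel and only the wording is at issue.

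The missing interval on r > .8 is a smaller matter. The point rule gives little protection just below .80 but more at .75. A reader might infer that the lower limit must exceed .8. That is a stricter choice, not a requirement of Hypothesis D: in simulation it passes only 49-64% of the time at true r .85, though at least 99.5% at .90.

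**What to change.** 1. Keep the correlation TOST. On the same 100 drawings and six raters, add:
   - the mean algorithm-minus-rater difference, with its 90% interval inside a bound fixed beforehand in score units (for example the ±.3 SD of Aim 1);
   - the SD ratio or slope;
   - an absolute-agreement ICC with its interval.

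   Treat the six raters as fixed and say that the result covers these raters only. Otherwise, limit the wording of section 2.3 and of Aim 2 in section 7 to rank agreement.
2. State which scores build the ROCFT and Clock norms, and use the score type that the product will report.
3. Report a confidence interval with the r > .8 result. Requiring its lower limit to exceed .8 is optional.

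**Cost.** Plan wording and a short analysis, with no new drawings or raters. With no true offset, the ±.3 SD check on fixed raters passes 99-100% of the time when raters differ in leniency by an SD of up to .2, and 92-97% at .3 (simulated, inter-rater r .85-.95). The limitation to these raters matters: with leniency SD .2 and a true offset of .3 SD from raters in general, the check still passes 23-32% of the time. The ±.3 SD is only an example. Under manual norms it corresponds to the 38th percentile for an average person, so a tighter bound may be preferred. The downside for the sponsor is that an algorithm may pass on ranking and fail on level.
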